#### List B:

- Increased work of breathing or respiratory rate (duration  $\geq 3$  days)
- New or increased adventitial sounds on lung examination (duration  $\geq 3$  days)
- Weight loss ≥5% decrease from highest value or decrease across 1 major percentile for age in past 6 months
- Increased cough (duration ≥3 days)
- Worked harder to breathe during physical activity (duration  $\geq 3$  days)
- Increased chest congestion or change in sputum (duration  $\geq$ 3 days)

It is recommended that LUM/IVA should not be interrupted during a pulmonary exacerbation unless, in the opinion of the investigator, it would be in the best interest of the subject.

The following information will be determined for protocol-defined pulmonary exacerbations:

- Number of pulmonary exacerbations
- Number of days with pulmonary exacerbations
- Time-to-first pulmonary exacerbation
- Number of pulmonary exacerbations requiring hospitalizations
- Number of days hospitalized for pulmonary exacerbations
- Time-to-first hospitalization for pulmonary exacerbation
- Number of pulmonary exacerbations requiring IV antibiotic therapy
- Number of days on IV antibiotic therapy for pulmonary exacerbations
- Time-to-first IV antibiotic therapy for pulmonary exacerbations

### 11.4.4.2 Hospitalization for CF

Subjects will be queried about planned and unplanned hospitalizations lasting ≥24 hours. The dates for hospitalizations and the reasons for hospitalizations will be documented.

If the hospitalization is unplanned, the procedures for safety reporting should also be followed (Section 13.1.2.3).

The following information will be determined:

- Number of planned hospitalizations for CF (i.e., prophylactic antibiotic therapy)
- Number of all unplanned hospitalizations
- Number of days of all unplanned hospitalizations
- Time-to-first unplanned hospitalization

### 11.4.5 Fecal Elastase-1

Stool samples for assessment of FE-1 will be collected at the study center during the study visit; however, samples may be collected by the subject's caregiver up to 24 hours before the study visit (e.g., at home) and brought to the study visit. Instructions for the collection, processing, and shipment of samples will be provided in a separate Laboratory Manual.

### 11.4.6 Immunoreactive Trypsinogen

Instructions for the collection, processing, and shipment of samples for assessment of IRT will be provided in a separate Laboratory Manual.

### 11.4.7 Microbiology Cultures

Specific instructions for the collection, processing, and shipment of samples for assessment of microbiology cultures will be provided in a separate Laboratory Manual.

### 11.4.8 Spirometry

See Section 11.6.7.

### 11.5 Efficacy

All efficacy-related assessments are listed in Section 11.4, Pharmacodynamics.

### 11.6 Safety

Safety evaluations will include AEs, clinical laboratory assessments (hematology, chemistry, coagulation studies, and urinalysis), clinical evaluation of vital signs, pulse oximetry, ECGs, PEs, spirometry, and OEs.

### 11.6.1 Adverse Events

All AEs will be assessed, documented, and reported in accordance with ICH GCP guidelines. Section 13.1 outlines the definitions, collection periods, criteria, and procedures for documenting, grading, and reporting AEs. A separate document that details AE case report form (CRF) completion guidelines for investigators as well as training will be provided.

### 11.6.2 Clinical Laboratory Assessments

The safety laboratory test panels are shown in Table 11-1. Additional clinical laboratory evaluations will be performed at other times if judged to be clinically appropriate. Laboratory test results that are abnormal and considered clinically significant will be reported as AEs (see Section 13.1).

**Table 11-1 Safety Laboratory Test Panels** 

Serum Chemistry	Hematology	Urinalysis a
Glucose	Hemoglobin	Leukocyte esterase
Blood urea nitrogen	Erythrocytes:	Nitrite
Creatinine	Mean corpuscular hemoglobin	Urobilinogen
Sodium	Mean corpuscular hemoglobin	Urine protein
Potassium	concentration	pН
Calcium	Mean corpuscular volume	Urine blood
Chloride	Platelets	Specific gravity
Magnesium	Reticulocytes (absolute)	Urine ketones
Bicarbonate	Leukocytes	Urine bilirubin
Inorganic phosphate	Differential (absolute and percent):	Urine glucose
Total bilirubin, direct bilirubin	Eosinophils	
Alkaline phosphatase	Basophils	
Aspartate aminotransferase (=SGOT)	Neutrophils	
Alanine aminotransferase (=SGPT)	Lymphocytes	
Lactate dehydrogenase	Monocytes	
Gamma-glutamyl transferase (GGT)	Coagulation Studies	
Total protein	Activated partial thromboplastin time	
Albumin	Prothrombin time	
Creatine kinase	Prothrombin time International	
	Normalized Ratio	

If urinalysis results are positive for leukocyte esterase, nitrite, protein, or blood, microscopic examination of urine will be performed and results will be provided for leukocytes, erythrocytes, crystals, bacteria, and casts.

For purposes of study conduct and data analysis, blood and urine samples will be analyzed at a central laboratory. However, at the discretion of the local investigator, samples may be analyzed at a local laboratory for management of urgent medical issues, including if a subject cannot return to the clinical study site for the mandatory liver function testing (Section 11.6.3). If a local laboratory test value is found to be abnormal and clinically significant, it will be verified by the central laboratory as soon as possible after the investigator becomes aware of the abnormal result. If it is not possible to send a timely specimen to the central laboratory (e.g., the subject was hospitalized elsewhere), the investigator may base the assessment of an AE on the local laboratory value.

#### **Elevation of Liver Function Test Parameters** 11.6.3

#### Mandatory Liver Function Testing

Liver function testing (alanine aminotransferase [ALT], aspartate aminotransferase [AST], gamma-glutamyl transferase [GGT], alkaline phosphatase [ALP], and total bilirubin) must be performed while subjects are receiving LUM/IVA treatment (see Table 3-1 and Section 11.6.2). These blood samples should be processed and shipped immediately per the Laboratory Manual.

Subjects with new ALT or AST elevations of  $\ge 3 \times \text{upper limit of normal (ULN)}$  and clinical symptoms will be followed closely, including repeat confirmatory testing performed by the central laboratory within 48 to 72 hours of the initial finding and subsequent close monitoring of ALT and AST levels, as clinically indicated. If a subject cannot return to the site for liver function testing, a local laboratory may be used. Elevations in LFTs (ALT or AST  $\geq 3 \times ULN$ ) at the local laboratory must be reported immediately to the medical monitor AND the subject must

have the tests repeated and sent to the central laboratory as soon as possible (ideally within 48 to 72 hours).

### **Study Drug Interruption**

LUM/IVA administration must be interrupted immediately, and the Vertex medical monitor or designee must be notified if any of the following criteria is met:

- ALT or AST  $> 8 \times ULN$
- ALT or AST  $\geq$ 5 × ULN for more than 2 weeks
- ALT or AST  $\ge 3 \times ULN$  in association with total bilirubin  $\ge 2 \times ULN$  and/or clinical jaundice

A thorough investigation of potential causes should be conducted, and the subject should be followed closely for clinical progression.

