### 12.3.4.2 Clinical Laboratory Assessments

For the laboratory measurements, the raw values and change from Cumulative Study Baseline of the continuous hematology and chemistry results will be summarized in SI units at each visit in the Cumulative Study Period.

For hematology and chemistry, the number and percentage of subjects with abnormal low (<lower limit of normal [LLN]) value and with abnormal high (>ULN) value at each scheduled time point in the Cumulative Study Period will be summarized.

The number and percentage of subjects with at least 1 categorical change during the Treatmentemergent Period of the Cumulative Study Period will be provided.

The categorical criteria will be provided in the SAP.

Results of urinalysis will be listed in individual subject data listings only. In addition, a listing containing individual subject hematology, chemistry, and coagulation values outside the reference ranges will be provided. This listing will include data from scheduled and unscheduled time points.

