#### **10.5.2 Clinical Laboratory**

For the laboratory measurements, the raw values and change from parent study baseline of the continuous hematology and chemistry results will be summarized in SI units at each visit in the Current Study Period (including all measurements from Study 116) for the overall group based on the 116 Safety Set.

For hematology and chemistry, the number and percentage of subjects with abnormal low (<lower limit of normal [LLN]) value and with abnormal high (>ULN) value at each scheduled time point in the Current Study Period will be summarized for the overall group based on the 116 Safety Set.

The number and percentage of subjects meeting the defined threshold criteria during the Treatment-emergent Period of the Current Study Period will be provided based on the 116 Safety Set. The threshold criteria are provided in [Appendix F](#).

Results of urinalysis will be listed in individual subject data listings only. In addition, a listing containing individual subject hematology, chemistry, and coagulation values outside the reference ranges will be provided. This listing will include data from scheduled and unscheduled time points.

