## Appendix F: Criteria for Threshold Analysis

**Table 13-5 Threshold Analysis Criteria for Laboratory Tests**

Parameter	Categorical change	Comments
Clinical Chemistry		
ALT	$\leq 3xULN$ *(Not a categorical change) $>3x - \leq 5xULN$ $>5x - \leq 8xULN$ $>3xULN$ $>5xULN$ $>8xULN$	FDA DILI Guidance Jul 2009.
AST	$\leq 3xULN$ *( Not a categorical change) $>3x - \leq 5xULN$ $>5x - \leq 8xULN$ $>3xULN$ $>5xULN$ $>8xULN$	FDA DILI Guidance Jul 2009.
ALT or AST	ALT $>3xULN$ or AST $>3xULN$	Vertex LFT working group 2014
ALT or AST	ALT $>5xULN$ or AST $>5xULN$	
ALT or AST	ALT $>8xULN$ or AST $>8xULN$	
Alkaline Phosphatase	$>1.5xULN$	FDA DILI Guidance Jul 2009.
Total Bilirubin	$>1.5x - \leq 2xULN$ $>2xULN$	FDA DILI Guidance Jul 2009.
ALT and Total Bilirubin	ALT $>3xULN$ and TBILI $>2xULN$	FDA DILI Guidance Jul 2009. To be counted within a same treatment phase, whatever the interval between measurements.
AST and Total Bilirubin	AST $>3xULN$ and TBILI $>2xULN$	FDA DILI Guidance Jul 2009. To be counted within a same treatment phase, whatever the interval between measurements.
(ALT or AST) and Total Bilirubin	(ALT $>3xULN$ or AST $>3xULN$ ) and TBILI $>2xULN$	Vertex LFT working group 2014
CPK	$>3x - \leq 10xULN$ $>10xULN$	FDA criteria Feb 2005. Am J Cardiol April 2006.
Creatinine	$\geq 150 \mu\text{mol/L}$ (Adults) $\geq 30\%$ change from baseline $\geq 100\%$ change from baseline	Benichou C., 1994.
Blood Urea Nitrogen	$\geq 17 \text{ mmol/L}$	
Chloride	$<85 \text{ mmol/L}$ $>115 \text{ mmol/L}$	
Sodium	$\leq 129 \text{ mmol/L}$ $\geq 150 \text{ mmol/L}$	

Potassium	<3 mmol/L ≥5.5 mmol/L	FDA Feb 2005.
Glucose		
Hypoglycaemia	≤3.9 mmol/L and <LLN	ADA May 2005.
Hyperglycaemia	≥11.1 mmol/L (unfasted); ≥7 mmol/L (fasted)	ADA Jan 2008.
Albumin	≤25 g/L	
Hematology		
WBC	<3.0 Giga/L (Non-Black); <2.0 Giga/L (Black) ≥16.0 Giga/L	Increase in WBC: not relevant. To be interpreted only if no differential count available.
Lymphocytes	>4.0 Giga/L	
Neutrophils	<1.5 Giga/L (Non-Black); <1.0 Giga/L (Black)	International Consensus meeting on drug-induced blood cytopenias, 1991. FDA criteria.
Monocytes	>0.7 Giga/L	
Basophils	>0.1 Giga/L	
Eosinophils	>0.5 Giga/L or >ULN (if ULN ≥0.5 Giga/L)	Harrison- Principles of internal Medicine 17th Ed., 2008.

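### SAP Table 13-5 counts ALT-with-bilirubin and AST-with-bilirubin elevations at any interval, leaves timing unstated on the combined row, and plans no concurrent count

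*Protocol*

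**What the plan says.** SAP Appendix F, Table 13-5 has three joint liver rows: ALT with total bilirubin, AST with total bilirubin, and ALT or AST with total bilirubin. All use transaminase >3x ULN and bilirubin >2x ULN.

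- The two single-enzyme rows carry the comment "To be counted within a same treatment phase, whatever the interval between measurements".
- The combined row carries only a source, "Vertex LFT working group 2014", and no timing rule.

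SAP 10.5.2 sets the counting period: "The number and percentage of subjects meeting the defined threshold criteria during the Treatment-emergent Period of the Current Study Period will be provided". Under SAP 9.1 that period runs from the first Study 116 dose to 14 days after the last dose, or to the last day in the study if earlier.

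Protocol 11.6.3 (Study Drug Interruption) also uses a joint condition: ALT or AST ≥3x ULN "in association with total bilirubin" ≥2x ULN and/or clinical jaundice. Its purpose is operational, since when it is met "LUM/IVA administration must be interrupted immediately". It gives no time window. For the analysis, Protocol 12.3.4.2 says "The categorical criteria will be provided in the SAP".

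**The concern.** A joint transaminase and bilirubin elevation is usually read as one hepatic episode. Under the any-interval rule, a child whose transaminases rose early and resolved, and who had an isolated bilirubin rise nearly two years later, is tabulated like a child with both on one sample. The table cannot tell a reader which occurred.

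This matters here because long-term safety is the primary objective, SAP 10.5.1 names elevated transaminases as an adverse event of special interest, and about 50 children are expected with no control arm against which to judge chance co-occurrence. One child is 1/50 = 2%.

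The silent combined row adds a separate problem. If a programmer applied any-interval counting to the single-enzyme rows and same-sample counting to the combined row, the combined count could come out below either of its components.

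**Working it through.** **1. How far apart can two counted values be?** The plan states no figure. The SAP does not define a treatment phase, so I take it to be the treatment-emergent period named in 10.5.2. Target days for chemistry (SAP Appendix C, counted from the first Study 116 dose) are 15, 85, 169, 253, 337, 505 and 673, with follow-up at 687. They agree with the schedule: 7 × 96 + 1 = 673, and 673 + 14 = 687.

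- Day 15 to Week 96: 673 − 15 = 658 days; 658/7 = 94.0 weeks.
- With the visit windows (±3 and ±7 days): (666 − 18)/7 = 92.6 to (680 − 12)/7 = 95.4 weeks.
- Day 15 to the follow-up target: (687 − 15)/7 = 96.0 weeks. This applies only to children who have that visit and whose draw falls within the 14-day limit.
- Under a same-sample rule: 0 weeks.

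**2. Which way does the rule err?** Any pair on the same sample also satisfies the any-interval rule. The any-interval count is therefore never below the concurrent count.

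**3. How large might the excess be?** The documents give no event rates, so every rate here is an assumption. Take 7 scheduled post-dose draws (Day 15; Weeks 12, 24, 36, 48, 72, 96) and 50 children. Let *a* be the per-draw chance of ALT or AST >3x ULN, and *b* that of bilirubin >2x ULN.

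With all elevations independent:

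- same draw, per child: 1 − (1 − ab)^7
- any interval, per child: [1 − (1 − a)^7] × [1 − (1 − b)^7]
- chance of at least one flagged child: 1 − (1 − p)^50, where p is the per-child probability

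| a | b | Expected, same draw | Expected, any interval | Ratio | At least one: same draw / any interval |
|---|---|---|---|---|---|
| 1% | 0.1% | 0.0035 | 0.024 | 6.8 | 0.3% / 2.3% |
| 3% | 0.5% | 0.052 | 0.33 | 6.3 | 5% / 28% |
| 5% | 1% | 0.17 | 1.02 | 5.9 | 16% / 64% |

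**4. What if the elevations are correlated within a draw?** Keep a = 3% and b = 0.5%. Let *c* be the chance of raised bilirubin on a draw with raised transaminase; independence is c = 0.5%. With j = ac:

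- same draw, per child: 1 − (1 − j)^7
- any interval, per child: 1 − (1 − a)^7 − (1 − b)^7 + (1 − a − b + j)^7

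For c = 2%, j = 0.0006. Same draw is 0.00419. Any interval is 1 − 0.80798 − 0.96552 + 0.78267 = 0.00917.

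| c | Expected, same draw | Expected, any interval | Ratio | Excess children |
|---|---|---|---|---|
| 0.5% | 0.052 | 0.33 | 6.3 | 0.28 |
| 2% | 0.21 | 0.46 | 2.2 | 0.25 |
| 5% | 0.52 | 0.71 | 1.4 | 0.19 |

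The ratio falls mainly because concurrent cases become commoner. The absolute excess at these rates moves only from 0.28 to 0.19 of a child.

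**The case against.** A reader might infer that the SAP contradicts the protocol. The documents do not support that. The Protocol 11.6.3 condition is an interruption trigger with no time window, and Protocol 12.3.4.2 hands the analysis criteria to the SAP. The natural sense of association is one episode, but the protocol sets no concurrent analysis definition for the SAP to depart from.

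A reader might also call every counted child a Hy's-law case. Neither document uses that term; Table 13-5 presents threshold criteria. Nor is the any-interval rule written on the combined row, where timing is simply unstated.

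A third inference is that children who met the protocol trigger cannot be traced. They largely can. SAP 10.5.1 lists adverse events leading to treatment interruption and summarises interruptions, discontinuations and serious events for the special-interest categories. SAP 10.5.2 lists out-of-range chemistry by child, scheduled and unscheduled. With about 50 children, hand checking is feasible.

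Finally, the rule misses no concurrent case, the study is descriptive, and SAP 10.5 plans no hypothesis test of safety data. All of this stands and limits the seriousness of the point. It does not change what the table reports: listings let a diligent reader reinterpret the count, but the tabulated number still mixes two kinds of event.

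**Conclusion.** The point holds as a weakness in an analysis choice and a gap in specification, not as a breach of the protocol. Two Table 13-5 rows can join values about 94 weeks apart (96 weeks at the follow-up target), the third has no timing rule, and no planned summary isolates concurrent elevations.

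The direction is certain: over-counting or no difference. The size is not. A sixfold excess should not be quoted as a finding, because it needs independence within a draw as well as assumed rates. At 3% and 0.5% per draw, modest correlation brings the ratio to 2.2 or 1.4. In absolute terms the middle case adds roughly 0.2 to 0.3 of an expected child, which still matters when one child is 2%.

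The cut-offs also differ. The protocol trigger uses ≥ and admits clinical jaundice; Table 13-5 uses > and omits jaundice. Neither the present rows nor an added concurrent row will therefore exactly match the children who met the trigger.

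**What to change.** In SAP Appendix F, Table 13-5:

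1. State the timing rule on all three joint rows, and say that the treatment phase means the Study 116 treatment-emergent period, if that is intended.
2. Add a concurrent count for each joint row, using the same sample or a short window that the sponsor prespecifies. The documents supply no window. After Day 15, scheduled chemistry targets are at least 85 − 15 = 70 days apart, so for scheduled draws a window of a few days acts as a same-sample rule.
3. Keep the any-interval count beside it, labelled as a screen.
4. List the dates of both values for every flagged child.
5. Reconcile the cut-offs and the jaundice element with Protocol 11.6.3, or add a note that the rows are not meant to reproduce the interruption trigger. This is about the analysis description only and takes no view on the clinical rule.

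The cost is SAP wording, one extra derived flag and a short listing, with no new data. The downside is that a true case whose transaminase and bilirubin peaks fall outside the chosen window appears only in the screening row, which is why that row should stay.

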### Resumption of Study Drug

If a convincing alternative etiology is identified for the elevated liver tests (ALT, AST, and total bilirubin), LUM/IVA may be resumed when levels return to baseline or are ≤2 × ULN, whichever is higher. Approval of the Vertex medical monitor or designee is required before resumption of LUM/IVA. Upon resumption of LUM/IVA, transaminases should be assessed weekly for 4 weeks. If a protocol-defined liver test elevation occurs within 4 weeks of rechallenge with LUM/IVA, then LUM/IVA must be discontinued, regardless of the presumed etiology.

### Discontinuation of Study Drug

If no convincing alternative etiology (e.g., acetaminophen use, viral hepatitis, or alcohol ingestion) for the elevated transaminases is identified, regardless of whether ALT or AST levels have improved, LUM/IVA treatment must be discontinued, after consulting with the Vertex medical monitor or authorized designee. Subjects in whom treatment is discontinued for elevated transaminases should have their transaminases monitored closely until levels normalize or return to baseline.

### 11.6.4 Physical Examinations and Vital Signs

A physical examination (PE) of all body systems and vital signs assessment will be performed at select study visits (see Table 3-1). At other visits, symptom-directed PEs and symptom-directed vital sign assessments can be performed at the discretion of the investigator or healthcare provider.

A PE includes a review of the following systems: head, neck, and thyroid; eyes, ears, nose, and throat (EENT); respiratory; cardiovascular; lymph nodes; abdomen; skin; musculoskeletal; and neurological. Breast, anorectal, and genital examinations will be performed when medically indicated. After screening, any clinically significant abnormal findings in PEs will be reported as AEs.

An abbreviated PE will be performed at some visits (see Table 3-1). The abbreviated PE will include an assessment of the following body systems: head/neck/thyroid, EENT, cardiovascular system, respiratory system, skin, and abdomen.

Vital signs include blood pressure (systolic and diastolic), temperature (oral), pulse rate, respiration rate, and pulse oximetry. The subject should rest for at least 5 minutes before having

vital signs measured; additional instructions will be included in a separate Study Reference Manual.

Weight and stature will be assessed and BMI will be derived. If subjects can stand unassisted and follow directions, stature should be measured as height; otherwise, stature will be measured as length. Stature and weight must be measured with shoes off and while wearing light clothing. BMI will be calculated using the following equation:

BMI 
$$(kg/m^2)$$
 = body weight  $(kg) \div stature^2 (m^2)$ 

### 11.6.5 Electrocardiograms

Standard 12-lead ECGs will be performed using a machine with printout. Standard 12-lead ECGs will be performed with central over-reading. All sites will be provided with ECG machine(s) and associated materials by the central ECG diagnostic service.

Additional standard 12-lead ECGs will be performed at any other time if clinically indicated. The performance of all ECGs will adhere to the following guidelines:

- The subject will be instructed to rest in the supine position for at least 5 minutes, if possible, before having an ECG performed.
- The ECG will be performed before any other procedures that may affect heart rate, such as blood draws.

A printout of the ECG traces will be made for safety review by the investigator and maintained with source documentation. Clinically significant ECG abnormalities occurring during the study through the end of study participation will be recorded as AEs.

A hard copy of the ECG will be printed and signed by the investigator at the site. To ensure the safety of the subjects, the investigator or designee at the investigator site will make comparisons to the predose measurement at Day 1 (baseline). If the QTcF is increased by >45 msec from the shortest baseline QTcF or the absolute QTcF value is >500 msec for any scheduled ECG, 2 additional ECGs will be performed approximately 2 to 4 minutes apart to confirm the original measurement. If either of the QTcF values from these repeated ECGs remains above the threshold value (>45 msec from baseline or >500 msec), a single ECG must be repeated at least hourly until QTcF values from 2 successive ECGs fall below the threshold value that triggered the repeat measurement.

If the QTc value remains above the threshold value (>45 msec from baseline or >500 msec) on repeated measurement or is noted on 2 or more occasions with no identified alternative etiology for the increased QTc, then discontinuation from LUM/IVA treatment may be required after discussion with the Vertex medical monitor or designee. Subjects who have treatment discontinued for increased QTcF should have their QTcF monitored closely until it normalizes or returns to baseline.

ECG data will be transmitted via modem to the central ECG diagnostic service. A cardiologist at the central ECG diagnostic service will review each ECG to confirm if intervals were calculated correctly and to provide an interpretation including a suggested clinical significance, as applicable. A report containing this information will be provided to the site for review and signature by the investigator. This report will be filed with the machine ECG report for each time point in the subject's source documents. The values reported by the central ECG diagnostic service will be used for data analysis.

